7.2.2.4 Laboratory Specimen Preparation, Handling, and Storage

Serum for antibody assays will be collected as described in the Schedule of Events ([Appendix A](#)). For samples scheduled to be collected during vaccination visits, samples will be collected before vaccination.

Peripheral blood mononuclear cell (PBMC) samples for MBC and T-cell assays will be collected as described in the Schedule of Events ([Appendix A](#)). For samples scheduled to be collected during vaccination visits, samples will be collected before vaccination. Plasma from the PBMC separations will be saved as described in the MOP.

Instructions for specimen preparation, handling, storage, and labeling are included in the MOP.

7.2.2.5 Laboratory Specimen Shipping

Specimen shipment will occur at intervals during this trial following all applicable International Air Transport Association (IATA) requirements and according to the specifics for storage temperature and documentation as detailed in the MOP.

8 ASSESSMENT OF SAFETY

8.1 Assessing and Recording Safety Parameters

Safety will be assessed by the frequency and severity of:

- Any AE related to 4CMenB immunization through the end of the study.
- Any AE related to rectal mucosal sampling procedures through the end of the study.
- Any SAEs through the end of the study.

8.1.1 Adverse Events

ICH E6 defines an AE as any untoward medical occurrence in a patient or clinical investigation subject administered a pharmaceutical product regardless of its causal relationship to the study treatment. FDA defines an AE as any untoward medical occurrence associated with the use of a drug in humans, whether or not considered drug related.

An AE can therefore be any unfavorable and unintended sign (including an abnormal laboratory finding), symptom, or disease temporally associated with the use of medicinal (investigational) product. In addition, AEs specific to the rectal mucosal biopsy cohort will be collected prior to study drug administration and are defined as any unfavorable and unintended sign, symptom, or disease temporally associated with the rectal mucosal biopsy procedure. The occurrence of an AE may come to the attention of study personnel during study visits and interviews of a study recipient presenting for medical care, or upon review by a study monitor.

All AEs, including solicited local (injection site) and systemic (subjective and quantitative) reactions, will be captured on the appropriate eCRF. Information to be collected for AEs includes event description, date of onset, assessment of severity, relationship to study product and alternate etiology (assessed only by those with the training and authority to make a diagnosis and listed on the Form FDA 1572 as an investigator), date of resolution, seriousness and outcome. AEs occurring during the trial collection and reporting period will be documented appropriately regardless of relationship. AEs will be followed through resolution.

8.1.1.1 Adverse Events Grading

All AEs (clinical symptoms) will be graded for severity and assessed for relationship to study product (see definitions). AEs characterized as intermittent require documentation of onset and duration of each episode. The start and stop date of each reported AE will be recorded on the

appropriate eCRF. Changes in the severity of an AE will be documented to allow an assessment of the duration of the event at each level of intensity.

Severity of Event:

AEs will be assessed by the investigator using a protocol-defined grading system (toxicity table included as an appendix). For events not included in the protocol-defined grading system, the following guidelines will be used to quantify severity:

- **Mild (Grade 1):** Events that are usually transient and may require only minimal or no treatment or therapeutic intervention and generally do not interfere with the subject's usual activities of daily living.
- **Moderate (Grade 2):** Events that are usually alleviated with additional specific therapeutic intervention. The event interferes with usual activities of daily living, causing discomfort but poses no significant or permanent risk of harm to the research participant.
- **Severe (Grade 3):** Events interrupt usual activities of daily living, or significantly affects clinical status, or may require intensive therapeutic intervention. Severe events are usually incapacitating.

Relationship to Study Product: The assessment of the AE's relationship to study product will be done by the licensed study physician indicated on the Form FDA 1572 and the assessment will be part of the documentation process. Whether the AE is related or not, is not a factor in determining what is or is not reported in this trial. If there is any doubt as to whether a clinical observation is an AE, the event should be reported.

In a clinical trial, the study product must always be suspect. The relationship to study product will be assessed for AEs using the terms related or not related:

- **Related** – There is a reasonable possibility that the study product caused the AE. Reasonable possibility means that there is evidence to suggest a causal relationship between the study product and the AE.
- **Not Related** – There is not a reasonable possibility that the administration of the study product caused the event.

8.1.2 Reactogenicity

Reactogenicity events are AEs that are common and known to occur following administration of this type of study vaccine. The Toxicity Grading Scale ([Appendix C](#)) will be used to grade solicited local (injection site) and systemic (subjective and quantitative) reactions.

8.1.3 Serious Adverse Events

An AE or suspected adverse reaction is considered a SAE if, in the view of either the site PI or sponsor, it results in any of the following outcomes:

- Death,
- a life-threatening adverse event¹,
- inpatient hospitalization or prolongation of existing hospitalization,
- a persistent or significant incapacity or substantial disruption of the ability to conduct normal life functions, or
- a congenital anomaly/birth defect.
- Important medical events that may not result in death, be life-threatening, or require hospitalizations may be considered serious when, based upon appropriate medical judgment they may jeopardize the patient or subject and may require medical or surgical intervention to prevent one of the outcomes listed in this definition. Examples of such medical events include allergic bronchospasm requiring intensive treatment in an emergency room or at home, blood dyscrasias or convulsions that do not result in inpatient hospitalization, or the development of drug dependency or drug abuse.

¹ Life-threatening adverse event. An AE is considered “life-threatening” if, in the view of either the site principal investigator or sponsor, its occurrence places the patient or subject at immediate risk of death. It does not include an AE that, had it occurred in a more severe form, might have caused death.

SAEs will be:

- Assessed for severity and relationship to study product or procedure and alternate etiology (if not related to study product) by a licensed study physician listed on the Form FDA 1572 or by the Institution as the site PI or Sub-Investigator.
- Recorded on the appropriate SAE eCRF.

- Followed through resolution by a licensed study physician (for investigational new drug application (IND) studies, a physician listed on the Form FDA 1572 as the site PI or Sub-Investigator).
- Reviewed and evaluated by DMID, an Independent Safety Monitor (ISM) (as deemed necessary), or Safety Monitoring Committee (SMC) (periodic review unless related), and the IRB/IEC.

8.2 Specification of Safety Parameters

Safety will be assessed by the frequency and severity of:

- Any AE related to 4CMenB immunization through the end of the study.
- Any AE related to rectal mucosal sampling procedures through the end of the study.
- Any SAEs through the end of the study.

8.2.1 Solicited Events

Solicited events are AEs that are common and known to occur following administration of study product. The Toxicity Grading Scale ([Appendix C](#)) will be used to grade solicited local (injection site) and systemic (subjective and quantitative) reactions. All subjects will complete a subject memory aid on the day of each vaccination through 7 days after each vaccination (i.e. Day 8 and Day 36 visits). Subject memory aids will be reviewed with the subjects for AEs (solicited injection site and systemic reactions, and unsolicited AEs). In addition, after each vaccination, whenever the subject is seen in the clinic or a phone call occurs (i.e., at all opportunities), solicited and unsolicited reactogenicity and AEs will be reviewed. Reactogenicity assessments will include an assessment of solicited AEs occurring from the time of each vaccination through seven days following each vaccination, which include injection site reactions (pruritus, erythema, ecchymosis, induration/swelling, pain, and tenderness) and systemic reactions (fever, chills/shivering/sweating, fatigue, malaise, myalgia and arthralgia (exclusive of the injection site), headache, and nausea).

Solicited injection site and systemic reactogenicity events will be documented and reported from Day 1 through Day 8 and Day 29 through Day 36,

8.2.2 Unsolicited Events

Unsolicited events are any other AEs that occur following rectal biopsy procedures or administration of study product. Unsolicited AEs will be collected and assessed through the end of the protocol-defined follow up period. Unsolicited AEs are followed through resolution or stabilization even if this extends beyond the reporting period.

8.2.3 Medically-Attended Adverse Events (MAAEs)

For each AE experienced, the subject will be asked if he/she had received medical attention, defined as hospitalization, an ER visit, or an otherwise unscheduled visit to or from medical personnel for any reason. AEs characterized by such unscheduled medical care will be designated as MAAEs.

8.3 Reporting Procedures

Any medical condition that is present at the time that the subject is screened will be considered as baseline and not reported as an AE. However, if the severity or frequency of any pre-existing medical condition worsens, it should be recorded as an AE.

If an event meets both the criteria of a study endpoint and an AE, the event will be reported either as a study endpoint or as an AE (not both).

For the rectal biopsy cohort, SAEs will be documented and reported from the time of the baseline rectal mucosal biopsy through approximately 6 months after the first study vaccination. For the non-rectal biopsy cohort, SAEs will be documented and reported from the first study vaccination through approximately 6 months after the first study vaccination.

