6.2 Enrollment

6.2.1 Visit 01, Day 1, Randomization and First Vaccination, Clinic Visit

The following activities will be performed at the first vaccination visit.

- Reconfirm the subject's willingness to participate before performing any study procedures, including their first vaccination.
- Review eligibility criteria, including results of HIV, RPR, and STI screening lab evaluations, with subjects before the first vaccination to assure continued eligibility.
- Review interim sexual history to identify any new sexual partners since the last screening visit. Subjects that report new sexual exposures should undergo repeat STI screening and enrollment should be deferred until results are available and assure continued eligibility.
- Review medical history and any updates obtained by interview of subjects since the last screening visit (Visit 00A or, if performed, Visits 00B and/or 00C) to assure continued eligibility.
- Review all concomitant medications and recent (within 28 days) vaccinations with subjects before the first vaccination for accuracy and completeness. Any new medications taken since the last screening visit (Visit 00A or, if performed, Visits 00B and/or 00C) will be recorded on the appropriate eCRF and assessed for continued eligibility.
- Review COVID-19 vaccine history to ensure the subject is at least 14 days out from any COVID-19 vaccine before receiving study vaccine.
- Assess all AE/SAEs and record them on the appropriate eCRF.
- Obtain vital signs including oral temperature, blood pressure, and pulse before the first vaccination. Perform a targeted physical examination as needed before the first vaccination, if indicated based on review of complete medical history and updates obtained by interview of subjects since the last screening visit (Visit 00A or, if performed, Visits 00B and/or 00C).
- Perform a urine pregnancy test within 24 hours before first vaccination on all female subjects of childbearing potential. Results must be negative and known before first vaccination.
- Collect blood samples for baseline immunologic assays as described in the Schedule of Events ([Appendix A](#))
- Collect rectal and oropharyngeal mucosal secretion samples for immunologic assays as described in the Schedule of Events ([Appendix A](#))
- From female subjects, collect vaginal mucosal secretion samples for immunologic assays as described in the Schedule of Events ([Appendix A](#))

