8.6 Halting Rules

8.6.1 Study Halting Criteria

The study will be halted for SMC review/recommendations if any of the following are reported:

- Any subject experiences an SAE after administration of study product that is considered related to study product.
- Any subject experiences an SAE after a study procedure that is considered related to the study procedure.
- An overall pattern of symptomatic, clinical, or laboratory events that the DMID Medical Monitor (MM) or SMC consider associated with the study product and that may appear minor in terms of individual events, but that may collectively represent a serious potential concern for safety.

If any of the halting rules are met, the study will not continue without a review of the safety data by and recommendation from the SMC before proceeding.

SMC retains the authority to suspend additional enrollment and administration of the study product during the entire study, as applicable.

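### AEs related to rectal sampling are a named safety parameter, but non-serious AEs get no procedure-relatedness judgement, and SAE reporting for the no-biopsy cohort opens after the Day 1 anoscopy

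*Protocol*

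**What the plan says.** **The parameter.** Protocol 8.2 lists "Any AE related to rectal mucosal sampling procedures through the end of the study". Protocol 8.1 and SAP 9.3 repeat it, and Protocol 3.1 says the final report will cover safety outcomes of mucosal sampling. SAP 4.5.2 leaves it out.

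**The procedures.** Under Protocol 7.1.1 every participant has rectal secretions taken through an anoscope, and the biopsy cohort also has two biopsy sessions. SAP 4.5.1 puts secretion sampling at Days 1, 29, 43, 57 and 181 and marks the Day 1 sample as pre-vaccination. Protocol 6.2.1 likewise lists "Collect rectal and oropharyngeal mucosal secretion samples for immunologic assays as described in the Schedule of Events" ahead of the injection.

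**Causality.** Protocol 8.1.1.1 states "All AEs (clinical symptoms) will be graded for severity and assessed for relationship to study product" and then "The relationship to study product will be assessed for AEs using the terms related or not related". The fields named in 8.1.1 include "relationship to study product and alternate etiology". Only 8.1.3, on SAEs, adds relatedness to a procedure.

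**Capture and definition.** Protocol 8.3 says "For the non-rectal biopsy cohort, SAEs will be documented and reported from the first study vaccination"; the biopsy cohort's window opens at the baseline biopsy. Protocol 8.2.2 says "Unsolicited events are any other AEs that occur following rectal biopsy procedures or administration of study product".

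**Halting.** One trigger in Protocol 8.6.1 is "Any subject experiences an SAE after a study procedure that is considered related to the study procedure".

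**Analysis.** Protocol 10.5.4 bases the safety evaluation on events from first study product onward. The Safety Population (Protocol 10.5.1.2, SAP 6.3.3) requires at least one dose.

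**The concern.** A safety parameter needs a variable that identifies its events, a period in which they are collected, a denominator and a table. For product-related AEs the plan has all four. For procedure-related AEs it has fragments.

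Three things are at stake. First, at Day 29 the anoscopy and dose 2 share a visit, so an event that either could explain is judged against the product only. Second, a biopsy complication before dose 1 may be recorded on the eCRF and still fall outside the protocol's analysis period. Third, a serious event between the Day 1 anoscopy and the injection lies outside the 8.3 window for the no-biopsy cohort. The halting rule acts only on what is reported. Someone withdrawn at that point and never dosed would enter neither the reporting window nor the Safety Population.

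**Working it through.** **1. Procedure counts.** The Table 1 cells give a no-biopsy cohort of 12 + 12 + 3 + 3 = 30 and a biopsy cohort of 8 + 8 + 2 + 2 = 20, total 50, matching the stated targets. These are approximate (maximum enrolment 60).

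- Anoscopies: 50 × 5 = 250, of which 30 × 5 = 150 in the no-biopsy cohort.
- Biopsy sessions: 20 × 2 = 40.
- All rectal procedures: 250 + 40 = 290.

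**2. What the stated windows leave out.**

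- Before the SAE window opens (no-biopsy, Day 1): 30 of 150 anoscopies = 20%, or 30/290 = 10.3% of all rectal procedures.
- Anoscopies performed with an SAE window open: 20 × 5 + 30 × 4 = 220 of 250.
- Before first dose, where the 10.5.4 analysis starts: 50 anoscopies + 20 baseline biopsies = 70 of 290 = 24.1%. That includes 20 of the 40 biopsy sessions.

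**3. Chance of a serious event in the Day 1 gap.** With risk p per procedure, P(at least one in 30) = 1 − (1 − p)^30.

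- p = 1/5000: 0.6%. Protocol 2.3.1 gives this as an upper figure for biopsy; using it for anoscopy is an assumption.
- p = 1/1000, assumed: 3.0%.

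Both count events with any onset time after those 30 procedures. Only an onset before the injection, or in someone then not dosed, is missed, so they are upper bounds at the given p.

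**4. Non-serious biopsy events.** Protocol 2.3.1 cites 16 related AEs in 1,004 research sigmoidoscopies (1.6%). If that applied here, 40 sessions would give 40 × 0.016 = 0.64 expected events. For the 20 baseline sessions, 20 × 0.016 = 0.32 are expected, with P(at least one) = 1 − 0.984^20 = 28%.

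**5. Relatedness, side by side.**

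- *SAEs:* product or procedure (Protocol 8.1.3).
- *Non-serious AEs:* product only (Protocol 8.1.1.1). SAP Tables 62 and 63 and Listing 25 carry relatedness to treatment and no procedure column. In Listing 25 the alternative etiology is given only when the event is judged not related to product, so an event called related to product shows nothing about the procedure.
- *Biopsy:* AEs from the procedure are recorded at Visits 00C, 00P and 06P. SAP Table 51 has a row for them, labelled as solicited events, but no solicited list (Protocol 8.2.1, SAP 9.3.1) contains a procedure event. Its N is the Safety Population, not the biopsy cohort or the procedures performed.
- *Anoscopy:* no dedicated record, row or denominator. The 24–48 hour call in Protocol 7.1.1 is for biopsy participants, and no contact is scheduled after the Day 181 anoscopy.

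**6. What a defined rate would show.** With no event in n procedures, the exact two-sided 95% upper limit is 1 − 0.025^(1/n).

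- n = 250: 1.46%, treating procedures as independent.
- n = 50 participants: 7.1%, which does not need that assumption.

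**The case against.** The strongest reply is that most of the pieces exist and the rest is an inconsistency to tidy. Several stronger readings that a reader might infer do fail.

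- *That no rate could ever be produced.* Biopsy AEs are recorded by source and Table 51 plans a count. Alternate etiology is collected for AEs and could identify some anoscopy events. What is missing is a prespecified variable and denominator, not every trace of the events. The eCRF is not among the documents, so a procedure item on the form cannot be ruled out.
- *That attribution is absent for all 250 anoscopies.* SAEs are already judged against procedure, and 220 of the 250 take place with an SAE window open. The gap in attribution concerns non-serious AEs.
- *That the unsolicited-AE definition excludes anoscopy events.* For a dosed participant, any other AE after dose 1 qualifies, and Protocol 8.1.1 documents AEs regardless of relationship. The omission matters only before dosing on Day 1.
- *That a fifth of serious anoscopy events in the no-biopsy cohort would be missed.* The 20% counts procedures. The uncovered time ends at the injection in the same visit.

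Visit 01 also says to assess all AE/SAEs, Protocol 8.3.1 requires any AE meeting a serious criterion to be submitted within 24 hours, and 8.6.1 sets no dosing condition. A site could follow these and report the event. But 8.1.1 ties AEs to product use and adds pre-dose collection only for the biopsy cohort, so the conflict is not resolved by the text.

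Finally, procedure-related AEs are not among the endpoints in Protocol 3.3.2, and the trial tests no formal hypothesis. That stands, and it limits the severity.

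**Conclusion.** The concern holds in a limited form. The parameter is named, yet the documents specify no procedure-relatedness judgement for non-serious AEs and no denominator or table for anoscopy events, so a complete and consistent rate is not defined. This is the main weakness and touches every planned anoscopy. Protocol 10.5.4, followed exactly, also omits AEs from the roughly 20 baseline biopsies.

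The SAE start for the no-biopsy cohort contradicts 6.2.1 and 8.6.1 and needs reconciling, but its likely effect is small: at most about 0.6% for any event at a risk of 1:5000. That rests on a biopsy figure applied to anoscopy. The exception is a person never dosed, for whom the whole follow-up is uncovered.

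Cohort sizes are targets, and the finding on attribution assumes the eCRF follows the protocol text. No immunogenicity conclusion is affected. This is a should-fix.

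**What to change.** 1. Reconcile Protocol 8.3 with 6.2.1 and 8.6.1 so that AE and SAE documentation starts at the first study procedure in both cohorts: the baseline biopsy, or the first procedure of Visit 01.
2. Add a related-to-study-procedure item for all AEs, answered separately from relatedness to product.
3. Name mucosal sampling in the unsolicited-AE definition (8.2.2), and allow for pre-dose procedure events in both cohorts in 8.1.1.
4. Align Protocol 10.5.4 and the population used for procedure AEs, so that pre-dose procedure events are counted, including those in people who are never dosed. An earlier start of reporting alone would not achieve this, because the Safety Population would still exclude them. Restore the parameter in SAP 4.5.2.
5. Replace the solicited biopsy row in SAP Table 51 with a defined procedure-related AE table, separate for anoscopy and biopsy, with participants and procedures performed as denominators and exact intervals. State that the per-procedure interval treats repeat procedures as independent.

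The cost is one eCRF field, reconciled wording in a few sections, one SAP table and a few more pre-dose events to record. Procedure attribution is best made when the event occurs; later reconstruction from etiology text would be incomplete.

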8.3.1 Reporting Serious Adverse Events

SAEs will be followed until resolution even if this extends beyond the study-reporting period. Resolution of an AE is defined as the return to pretreatment status or stabilization of the condition with the expectation that it will remain chronic.

Any AE that meets a protocol-defined serious criterion must be submitted immediately (within 24 hours of site awareness) on an SAE form to the DMID Pharmacovigilance Group, at the following address:

DMID Pharmacovigilance Group

Clinical Research Operations and Management Support (CROMS)

[name] [REDACTED]

[name]

SAE Hot Line: [REDACTED]

SAE FAX Number: [REDACTED]

SAE Email Address: [REDACTED]

In addition to the SAE form, select SAE data fields must also be entered into the data coordinating center (DCC) system. Please see the protocol-specific MOP for details regarding this procedure.

Other supporting documentation of the event may be requested by the DMID Pharmacovigilance Group and should be provided as soon as possible.

The site will send a copy of the SAE report(s) to the DMID Pharmacovigilance Group. The DMID Medical Monitor and DMID Clinical Project Manager will be notified of the SAE by the DMID Pharmacovigilance Group. The DMID Medical Monitor will review and assess the SAE for regulatory reporting and potential impact on study subject safety and protocol conduct.

At any time after completion of the study, if the site principal investigator or appropriate sub-investigator becomes aware of an SAE that is suspected to be related to study product, the site PI or appropriate sub-investigator will report the event to the DMID Pharmacovigilance Group.

